## 7.3 Statistical Analysis Plan

A detailed statistical analysis plan will be developed before database closure.

For all the key parameters recorded, summary tables including descriptive and/or distribution statistics will be given for both the per-protocol analysis and the safety data sets.

All participants who meet the eligibility criteria, adhere to the protocol, and successfully complete the full study assessment will be available for the per-protocol analysis. Participants with missing data will be included in the analysis unless there is some non-response-related reason to exclude them, such as a protocol violation/invalid data.

For continuous variables, the following descriptive statistics will be reported: mean, median, standard deviation, quartiles, minimum, maximum and sample size. For nominal and ordinal variables distribution tables will be produced.

Normality testing will be performed for endpoints variables. All the continuous/ordinal endpoints analysed by way of comparative statistics will be checked for normality. The kurtosis and skewness values will be produced. The Q-Q Probability plot will be used to examine the values against the normal distribution. Statistical testing by Kolmogorov Smirnov and Shapiro Wilk tests will also be considered. If the normality assumption holds, a Linear Mixed Model will be used while, if the normality assumption does not hold, a Generalized Linear Mixed Model will be used.

For the primary analyses, the 2-sided 95% confidence interval for the difference between the test and control lenses will be produced, with non-inferiority being shown if the interval is entirely above -10.0 points for overall visual satisfaction and -2.0 hours for daily wearing time.

For the secondary analyses, the 2-sided 95% confidence interval for the difference between the test and control lenses will be produced, with non-inferiority being shown if the interval is entirely below +0.05 logMAR points for overall visual performance and if the interval is entirely above -10.0 points for specific activities visual satisfaction.

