### **12.5 Unmasking of Study Information**

Masked information on the identity of the assigned study product(s) should not be disclosed during the study unless there are medical or safety reasons to do so, for example knowledge of the product may be necessary for the treatment of some adverse events. The randomisation and masking data is under the control of a designated unmasked member of staff. In the event of any adverse event requiring unmasking, the identity of the product can be requested by the Investigator, Medical Monitor or any medical personnel. In the event that unmasking occurs, the following should be recorded:

- i. The ID of the unmasked participant,
- ii. The reason for unmasking,
- iii. The study staff person responsible for unmasking,
- iv. A list of person(s) who have been unmasked.

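### Section 7.3 lets normality of the endpoint values, rather than of model residuals, choose between a linear mixed model and a GLMM for the non-inferiority intervals

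*Combined protocol and SAP*

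**What the plan says.** Section 7.3 states what is tested: "Normality testing will be performed for endpoints variables". It then sets the scope: "All the continuous/ordinal endpoints analysed by way of comparative statistics will be checked for normality". Skewness and kurtosis are to be produced, and the graphical check is on the values themselves: "The Q-Q Probability plot will be used to examine the values against the normal distribution". Formal tests are optional: "Statistical testing by Kolmogorov Smirnov and Shapiro Wilk tests will also be considered". If normality holds, a linear mixed model is fitted; "if the normality assumption does not hold, a Generalized Linear Mixed Model will be used".

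The same section takes the non-inferiority decision from a two-sided 95% interval for test minus control, "non-inferiority being shown if the interval is entirely above -10.0 points for overall visual satisfaction and -2.0 hours for daily wearing time". The secondary endpoints are handled in the same way, with limits of +0.05 logMAR for acuity and -10.0 points for activity-specific satisfaction. The section opens by deferring detail: "A detailed statistical analysis plan will be developed before database closure".

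The Synopsis describes a randomised-order crossover in which each participant wears three lens types. Section 7.2 sizes the trial from the SD of the test-control difference (16.1 points for overall satisfaction) and aims for at least 20 per-protocol participants.

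**The concern.** A linear mixed model does not need normally distributed outcome values. Its assumptions concern the residuals and the random participant effects. For a participant who wears all three lenses, the participant effect cancels from test minus control, so its shape does not affect that contrast. What matters is the within-participant error.

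The values mix both sources. Visual satisfaction on a 100-point scale may well cluster near the top, and some participants score high or low on every lens. Either feature can make the values look non-normal while the residuals and differences are close to normal. The plan would then leave a suitable model for a reason unrelated to its suitability, and the model behind a primary decision would depend on a data-driven check.

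**Working it through.** **1. The plan's own calculation already uses the within-participant difference.** Section 7.2 gives SD of difference 16.1, margin 10, true difference 0 and one-sided level 0.025. For a paired t-test,

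power = 1 - F(t[0.975, n-1]; n-1 df, noncentrality = (10/16.1)·√n),

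where F is the noncentral t distribution function. At n = 23 the noncentrality is 0.621 × 4.796 = 2.98 and power is 81.2%. At n = 22 power is 79.3%. The stated 23 is therefore reproduced as the smallest n reaching 80%. It depends on the distribution of the differences, not of the values.

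**2. Why the participant effect drops out.** Write a score as y = mean + lens + period + b + e, with participant effect b and within-participant error e. For one participant, test minus control = lens difference + period difference + (e_test - e_control). The term b is gone, but it remains in every value that the Q-Q plot and the tests would examine.

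**3. How often each check fails.** From the documents: three lenses, n = 20, SD of difference 16.1, which corresponds to a within-lens SD of 16.1/√2 = 11.4. Assumed, because the documents give no figure: participant SD 12, a second within-lens SD of 13, normal latent scores rounded and capped to 0-100, latent mean 60 to 85, and a 5% test level. With equal lenses and 4,000 trials per setting, Shapiro-Wilk rejects as follows (ranges cover the two within-lens SDs):

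| Latent mean | Values pooled over lenses | Values of one lens | Paired differences | Model residuals |
|---|---|---|---|---|
| 60 | 5.3-5.8% | 4.0-4.4% | 4.5-5.3% | 2.7-3.1% |
| 70 | 12.4-16.6% | 4.3-4.8% | 4.3-4.8% | 3.0-3.6% |
| 80 | 70.5-81.3% | 18-22% | 5.6-5.8% | 4.3-4.4% |
| 85 | 95.2-97.8% | 46-52% | 7.1% | 7.4-8.3% |

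Allowing for repeat runs, the ranges at mean 80 are about 70-81% pooled, 16-24% for one lens, and 4-6% for residuals or paired differences.

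**4. A case where the differences are exactly normal.** Take left-skewed (exponential) participant levels with SD 20, normal errors giving SD of difference 16.1, n = 20 and no cap. Shapiro-Wilk rejects in 64% of trials on pooled values and in 59% for at least one of the three lenses. For at least one of the two differences it rejects in 10%. Two independent 5% tests would give 1 - 0.95² = 9.75%, so the last figure is simply the nominal rate.

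**5. Does the linear model need rescuing?** Set the true loss on the capped scale to exactly 10 points and fit lens + period + participant. Residual df = 60 - (1 + 2 + 2 + 19) = 36. The lower limit of the 95% interval should exceed -10 in 2.5% of trials. Over eight settings (four means, two within-lens SDs; 40,000 trials each) it did so in 2.32-2.54% per lens; a repeat over the eight settings gave 2.1-2.5%.

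Among trials failing the pooled check, the linear model's error was 2.2-2.8% where failure was common (means 80 and 85). Where failure was rare (means 60 and 70; 546-713 trials) it was 2.8-4.1%, with standard error about 0.6-0.8 points. The highest of these is about (4.1 - 2.5)/0.8 = 2 standard errors above nominal, in too few trials to settle whether there is a small excess.

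**The case against.** **The text never says raw values.** True. It speaks of endpoint variables and of values, and a sympathetic reader could take the normality assumption to mean that of the model, hence residuals. Nor does it expressly say that the interval comes from the selected model. But residuals and differences are not mentioned, and no other comparative model is named. The finding therefore rests on the plain reading; if residuals were meant, the text should say so.

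**A detailed SAP is still to come.** This disposes of part of the complaint. The test level, which tool decides, and the GLMM family and link are ordinary contents of that document. It does not undo a switch, and an object of testing, that section 7.3 already states.

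**The size depends on choices the plan does not make.** This stands. Pooling over lenses gives the largest figure, and one lens's values give much less. At a mean of 60 the check fires at about its nominal rate. A reader might also infer that the named tools will usually contradict each other. At mean 80, Shapiro-Wilk rejects while Kolmogorov-Smirnov does not in 69-81% of trials with the uncorrected p-value, but in 51-53% with the Lilliefors correction. The plan does not say which version applies, so this supports no firm claim.

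**The decision scale is fixed.** A reader might infer that a GLMM would test the margin on the wrong scale. The documents do not support that: section 7.3 already requires a difference in points, hours or logMAR, and an identity link would deliver it directly. Only a non-identity link, which the plan does not choose, would need a stated route back.

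**Conclusion.** The concern holds as a modest but real fault in a stated rule: section 7.3, read plainly, uses the wrong diagnostic to choose the model for the non-inferiority intervals. For satisfaction scores with a latent mean near 80, the values would fail Shapiro-Wilk several times as often as the residuals or differences: about 70-81% pooled or 16-24% for one lens, against 4-6%. These rates show direction and rest on the assumed mean, SDs, cap and test level. With scores centred near 60 there is little contrast.

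A reader might go further and infer that the switch inflates the chance of a false non-inferiority claim. That has not been shown. Neither the GLMM branch nor the two-stage procedure was simulated, and no changed conclusion was found. What has been shown is narrower: for the VAS endpoint, in all eight settings, the linear model alone held about 2.1-2.5% overall against a nominal 2.5%, so the switch was not needed for validity there. Wearing time and logMAR acuity were not simulated; for them the argument rests on the model's assumptions, not on figures.

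**What to change.** In section 7.3, pre-specify the linear mixed model on the original scale, with fixed effects for lens and period and a random participant effect. Make it the single primary analysis for the continuous non-inferiority endpoints: overall and activity-specific satisfaction, wearing time and logMAR acuity. Remove the normality-driven switch. Examine model residuals, not the endpoint values, and treat the result as a diagnostic that does not change the analysis.

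If a robustness analysis is wanted, name one in advance that gives test minus control in points, hours or logMAR, and report it whatever the diagnostics show. The method, for example a bootstrap, is for the sponsor to choose. A GLMM may remain for truly ordinal endpoints.

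Finalise this before anyone making analysis decisions sees unmasked data. Section 12.5 helps, since apart from medical or safety reasons "Masked information on the identity of the assigned study product(s) should not be disclosed during the study". The cost is SAP wording and, at most, one small extra table.

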## 8 Risk Analysis

### 8.1 Site Specific Risk Analysis

[REDACTED] has conducted a risk and benefit analysis of this study being carried out at its [REDACTED] following the site SOPs in place to carry out clinical studies. Details of the analysis is detailed below. [REDACTED]  
[REDACTED]  
[REDACTED]

### 8.2 Benefits

The direct benefit to the participants, who will all be myopic adolescent, will be the opportunity to try different contact lens types to potentially manage their myopia progression. At the end of the study this direct experience will help them in deciding if wearing multifocal soft contact lenses to manage their myopia progression is an optical correction they would consider using. Contact lenses also offer improved side vision, less optical distortion compared to spectacles and the convenience of not wearing spectacles.

The additional benefit for the myopic adolescent population is the determination of the contact lens types that can be incorporated in a long-term study to identify the most efficient designs to control myopia progression. Children myopia is an underestimated epidemic currently lacking solution to stop that progression, hence, the urgent need to improve upon the current solutions available. In this context, controlling myopia progression is not only to do with making the adolescent less reliant on the need of wearing a refractive correction or wearing a refractive correction of a lesser power. The presence of myopia is associated with an increase of the risks of developing ocular pathology in adulthood [REDACTED].

In addition, participants will receive an examination of the front part of their eyes and may have the opportunity to try different types of contact lenses at no cost to them.

### 8.3 Risks

All the assessments are routine clinical and specialist procedures, and none present any increased risk to participants compared with normal clinical routine.

All the study lenses are CE marked and approved for daily wear use for the correction of presbyopia in adults. Daily wear modality of soft contact lenses (the lenses will be removed every night and cared for with the lens care solution provided) have demonstrated good safety in decades. To make a valid assessment of the safety of soft contact lenses in children, researchers have compared a number of different studies [4] where the children (age 7 to 17 years old) were wearing contact lenses over one- or two-years period. Four of the six studies [5-8] observed no corneal infiltrative events, but the 95% confidence intervals can still be estimated. The upper limit never exceeds 300 per 10,000 patient years. The summarised incidence of corneal infiltrates in children teenagers and adults showed that the incidence of corneal infiltrative events in children is markedly lower than in adults [10]. The prospective studies of children represent over 2,000 patient years

of soft contact lens wear. Combining the six prospective studies, the estimated incidence of corneal infiltrative events in children is per 54 per 10,000 patient years and the upper 95% limit is 86 per 10,000 patient years. Therefore, each year, no more than 86 cases of corneal infiltrative events per 10,000 patients. In contrast, the expectation will be 300 in adults. The frequency of adverse events is lower in children compared to university students and young adults. The likelihood of microbial keratitis is negligible, with no reported cases in over 2,000 prospective and 400 retrospective patient years of lens wear [REDACTED].

Vigilance is still needed in spite of the low incidence of microbial keratitis in children. Education is key. All participants will be educated about the importance of good hygiene and list risky behaviours that can have consequences. Participants with an uncomfortable red eye will be seen promptly and managed appropriately. Complications may occur due to non-compliant behaviour. Behaviours related to increased risk of contact lens-related infections were much more common in teenagers and adolescents included showering and sleeping in lenses, with the latter increasing when travelling, drinking, and being away from home. This will be mitigated by the investigator providing information to the participants and parents/guardians reinforcing what they can and cannot do with contact lenses prior to dispensing. The participants will be under the care of the research investigators for the duration of the study period and the investigators will be present to deal with any unexpected event. Further, a medical monitor is appointed for this study. The medical monitor will receive and review any adverse events and may stop the study in the event that he identifies an abnormal trend. The medical monitor will also be available to rapidly treat any adverse event requiring medical management.

Vision with the study contact lenses may not be as good or clear as with spectacles. The participants vision with the study contact lenses will be measured prior to the participants leaving the clinic to ensure that their vision is satisfactory and achieves the required standard for dispensing.

Children 12 years and younger have demonstrated that they can handle contact lenses [REDACTED]. In this study, some of the participants will be existing contact lens wearers. For non-contact lens wearers, they (including parents/guardians) will be shown how to handle and care for the contact lenses. The use of soft contact lenses in adolescent, either to simply correct myopia with spherical contact lenses or retarding myopia using multifocal contact lenses is part of the management of myopia in [REDACTED] practice and several contact lenses are CE marked for that application. A contact lens alternative to control myopia is the use of rigid gas permeable contact lenses overnight during sleep; the implementation of the modality of myopia progression control is also approved but carries significant greater risk of unwanted effects than the modality followed in this study.

It is possible that the following problems may occur with the use of contact lenses; feeling that something is in the eye such as a foreign body or scratched area; excessive watering (tearing) of the eye; unusual eye secretions; redness of the eye; reduced sharpness of vision, blurred vision, rainbows, or halos around objects; sensitivity to light (photophobia); or dry eyes. These complaints will be closely monitored during the study and if the participant experience any of these, they have been informed that they should contact the study investigator as soon as possible. In rare instances, corneal ulcers, scarring, the growth of blood vessels into the cornea, temporary or permanent decreased vision, iritis and infections of the eye requiring treatment might occur.

In the event of any problem or concern the participants and parents/ guardians will be informed at the time of dispensing that they should contact the clinic during clinic hours or call the 24 hours emergency number they have been given.

The participants will have their vision checked at the onset of the study and prior to exiting the study to ensure that vision with contact lenses remain unchanged.

#### 8.4 Conclusion

[REDACTED] the proposed clinical investigation, based on the users and products effectiveness risks and the risk management strategy in place (preventative and corrective), given that the severity of problems will be mostly minor, non-permanent and the likelihood of occurrence is unlikely with likelihood of non-detection if problem occurs being low, this study is justified as the overall potential benefit to the population outweighs its risks.

## 9 Adverse Events and Reporting

### 9.1 Adverse Events

Adverse events including serious adverse events and quality complaints will be reported in accordance with ICH E6 Guideline for Good Clinical Practice. Adverse event reports to the Independent Ethics Committee and MHRA will be made according to their requirements.

#### 9.1.2 Normal or Adaptive Symptoms

---

Transient symptoms such as end-of-day dryness, lens awareness, itching or burning or other discomfort may occur with contact lens wear and may occasionally reduce wearing time. These are not reported as adverse events unless in the investigator's opinion they are unexpected in nature, severe or have a high rate of occurrence.

This clinical study will also ascertain satisfaction or preference with participative attributes such as comfort, vision, or lens handling. Responses to these participative questionnaires will not be considered as Adverse Events, complaints or Device Malfunctions.

### 9.1.3 Procedures for Adverse Events

Treatment of an adverse event will depend on its nature and severity. Based on the clinical judgment of the investigator the participant may be referred to an ophthalmologist for treatment. The investigator will attempt to determine whether the reaction is related to the contact lenses or a result of other factors. An Adverse Event Form will be completed for each adverse event. If both eyes are involved, each eye will be counted as one adverse event and Adverse Event information will be completed *for each eye*. Whenever possible, the adverse event will be photo-documented.

Expenses incurred for medical treatment as part of study participation will be paid by the sponsor (bills and prescription receipts kept). The participant must be followed until resolution and a written report completed indicating the subsequent treatment and resolution of the condition.

## 11 Investigator, Sponsor and Medical Monitor Responsibilities

### 11.1 *Investigator Responsibilities*

The investigator is responsible for ensuring participant safety and data quality by: protocol compliance, adherence to GCP and local regulatory requirements, and the Declaration of Helsinki. The investigator should

be appropriately qualified and legally entitled to practice and be trained in the proper method of obtaining informed consent.

The investigator must have the appropriate resources to conduct the clinical trial, be familiar with the protocol and agree to adhere to it, support monitoring and auditing activities, communicate with the Sponsor regarding any clinical trial issues or need for protocol modifications, make the necessary arrangements to ensure proper conduct and completion of the clinical trial, and ensure the protection and welfare of the participant, including arranging any emergency treatment as needed.

The investigator must ensure written Ethics Committee approval is received prior to the start of the clinical trial, that the Ethics Committee and sponsor is kept informed of the clinical trial progress, including serious/adverse events and deviations as required by them, and that any changes to the protocol are notified to the Ethics Committee and review written approval prior to implementation.

The investigator must try to ensure adequate participant recruitment; that all necessary and appropriate information is given to potential participants to ensure informed consent; is taken and documents; and that clinical records indicate the participant is enrolled in a clinical trial. The investigator must ensure that participants are provided with emergency contact details along with a procedure to follow in the case of an emergency, and that participants are kept informed as pertinent new information becomes available that may affect their decision to participate.

The investigator has primary responsibility for the accuracy, legibility and security of all clinical investigation data, video recordings, documents and participant records at the Investigator site during and after the clinical trial. CRFs are to be signed by the investigator, and any alterations to data are to be made by authorized personnel, initialled and dated by same or, in the instance of electronic data, an audit trail will be in place, with no obstruction of the original data.

The investigator must ensure that data be kept for the minimum time as specified by this protocol. The test product must be accounted for (the quantity of the devices received must be reconciled with the quantities of the device used, discarded or returned), and must also be responsible for the supervision and assignment of duties to all responsible for the conduct and evaluation of the clinical trial for the Investigator centre involved

